#### II. INTRODUCTION

It is well known that the removal and prevention of bacterial plaque by good oral hygiene is necessary to achieve and maintain oral health. Several studies have shown the role of plaque in the etiology of gingivitis . Clinical studies have also shown that effective control of supragingival plaque is important in the prevention of periodontal disease.

A series of clinical studies have evaluated the use of	baking soda dentifrices for their effect on plaqu					
removal. These studies, which include five single-brushing studies	 and a 4-week plaque removal study  , have shown					
the plaque removal benefits of baking soda-containing dentifrices. Brushing with						
toothpaste, containing 20% sodium bicarbonate,	was consistently shown to be more effective in					
enhancing plaque removal as compared to various non-baking sod	a toothpastes. Therefore					
is interested in exploring the long-term efficacy of brushing with						
toothpaste in subjects with existing plaque and gingivitis.						
A double-blind, randomized, 12-week, observational clinical study	y evaluated and compared the efficacy of two					
commercially available dentifrices, a baking soda containing denti	frice (					
, containing 20% sodium bicarbonate) and a regular non-ba	aking soda dentifrice (					
Regular Paste - negative control), for their ability to reduce gingive	ritis and enhance supragingival plaque removal.					
Results showed that	gnificantly (p<0.001) more effective in reducing					
gingivitis, bleeding and plaque than Tooth	paste following 4-, 8- and 12-weeks of product use.					
Based on the results of the 12-week pilot study, this 6-month defir	nitive clinical study will evaluate and compare the					
efficacy of two baking soda-containing dentifrice	es, containing 20% & 35% baking soda, to a non-					
baking soda dentifrice for their ability to reduce gingivitis and place	que following 6-months of use.					

#### STUDY OBJECTIVES

The objectives of this 6-month clinical research study are:

- 1) Primary objective is to evaluate the safety and efficacy of two baking soda dentifrices, containing 20% and 35% baking soda, (test products) compared to that of a non-baking soda dentifrice (negative control) in reducing gingival inflammation and bleeding.
- 2) Secondary objective is to evaluate the efficacy of two baking soda dentifrices compared to that of a non-baking soda dentifrice in reducing plaque.

#### III. INSTITUTIONAL REVIEW BOARD OR INDEPENDENT ETHICS COMMITTEE

Approval from an Institutional Review Board/Independent Ethics Committee is required prior to initiation of the study. A copy of the approval letter and approved documents will be provided to the Sponsor. The IRB/IEC will review the protocol, the informed consent, safety information, subject instructions, compliance diary, subject compensation and any amendments.

The investigator shall not request the written informed consent of any subject to participate, and shall not allow any subject to participate in the study prior to obtaining IRB/IEC approval of the study.

All protocol amendments need IRB approval prior to implementation and will not be instituted until the amendment and revised informed consent (if applicable) have been reviewed and received approval/favorable opinion from the local IRB/IEC. A protocol amendment intended to eliminate an apparent immediate hazard to subjects may be implemented immediately if the IRB/IEC are notified as soon as possible and an approval is requested. Protocol amendments exclusively for logistical or administrative changes may be implemented with notification to the IRB/IEC only.

The constitution of the IRB/IEC must meet the requirements of ICH GCP and of the participating country/countries. A list of IRB/IEC members who attended the meeting when the CTP/CTP amendment was discussed, including the names and qualifications, needs to be provided by the IRB/IEC to the investigator along with a statement from the

IRB/IEC that it is organized per GCP and the applicable laws and regulations. The IRB/IEC must perform all duties outlined by the requirements of ICH GCP and of the participating country/countries.

At the conclusion of the study, the Investigator must submit a study closeout form to the IRB/IEC with a copy forwarded to the Sponsor no later than 60 days after the close of the study. In addition, the response from the IRB/IEC, regarding study closeout will be forwarded to the Sponsor.

#### IV. SUBJECT INFORMATION AND CONSENT

The clinical investigation, including the consent form, will be reviewed by an IRB/IEC in accordance with Title 21 of the Code of Federal Regulations, Parts 50 and 56 and in accordance with local regulatory and legal requirements of Health Canada. Subjects must sign and date an Informed Consent consistent with requirements specified in the U.S. Code of Federal Regulations (21 CFR Parts 50, 56, 312, the International Conference on Harmonization (ICH)/Good Clinical Practice (GCP) guidelines and any local regulatory and legal requirements of Health Canada prior to participation in the trial. Subjects will be given ample opportunity to read the consent form and to have all questions regarding study conduct answered prior to signing and dating the consent form. Each subject will be provided with an exact copy of the informed consent form to retain for his or her records.

Informed consent means the knowing consent of an individual, to exercise free power of choice without undue inducement or constraint or coercion. The elements of information necessary for such consent include: a statement that the study involves research; an explanation of the procedures to be followed and their purpose; identification of any procedures that are experimental; any expected discomforts, risks or benefits; approximate number of subjects involved in the study; any appropriate alternative procedures or treatments; description of the confidentiality of subject records; name and phone number of the individual to contact with inquiries concerning the research; explanation of compensation or free medical treatment available for research-related injury; statement that the subject is free to withdraw consent and to discontinue participation at any time; statement that participation is voluntary; indication of any additional costs to the subject; assurance that the subject will be notified of new findings relevant to the subject's participation; statement that it is within the Investigator's discretion to drop the subject from participation at any time.

In addition, the informed consent should include no exculpatory language by which the subject is made to waive, or appear to waive, any of his/her legal rights or to release the institution from liability or negligence.

#### V. SUBJECT POPULATION

#### **Number of Subjects**

Approximately 320 subjects will be enrolled to ensure that 100 subjects per group (300 total) will be expected to complete the 6-month study. Subjects will be selected from the study site's database of subjects located in the Mississauga, Ontario area. Volunteers must read and sign the Informed Consent Form after the nature of the study has been fully explained.

#### **Inclusion Criteria**

Individuals may be included in the study provided they meet all the following inclusion criteria:

- Have provided written informed consent prior to being entered into the study.
- Be between 18 and 70 years of age, male or female.
- Have at least eighteen (18) natural teeth with scorable facial and lingual surfaces as determined by the Examiner. Teeth that are grossly carious, orthodontically banded, exhibiting general cervical abrasion and/or enamel abrasion, or third molars will not be included in the tooth count.
- Have a mean baseline plaque index score ≥ 1.95 as determined by the Soparkar Modification of the Turesky Modification of the Quigley-Hein Plaque Index (PI).
- Have a mean baseline gingival index score of ≥ 1.70 and ≤ 3.0 as determined by the Modified Gingival Index (MGI).
- Presence of  $\geq 10$  bleeding sites upon probing.
- Agree not to have a dental prophylaxis or any other elective, non-emergency dental procedures any time during the study.

- Agree to abstain from the use of chewing gum, mouth rinses, any toothpaste other than the study toothpaste, tooth whitening products (either professional or at home use) and all other oral hygiene other than the study procedures for the duration of the study.
- Agree to refrain from all oral hygiene on the morning of each evaluation visit and to refrain from eating, drinking and smoking for 4 hrs. prior to each evaluation visit.
- Agree to comply with the conditions and schedule of the study.

#### **Exclusion Criteria**

Individuals are not eligible for participation in this study if any of the following are noted:

- Physical limitations or restrictions that might preclude normal tooth brushing.
- Evidence of gross oral pathology, including widespread caries or chronic neglect, extensive restoration, preexisting gross plaque or soft or hard tissue tumor of the oral cavity.
- Heavy supra- or subgingival calculus that might interfere with evaluations as determined by the Investigator/Examiner.
- Evidence of major oral hard or soft tissue lesions or trauma at the baseline visit as determined by the Investigator/Examiner.
- Conditions requiring antibiotic treatment prior to dental procedures.
- History of uncontrolled diabetes or hepatic or renal disease, or other serious conditions or transmittable diseases, (e.g. cardiovascular disease, AIDS).
- Subjects with grossly carious, fully crowned, or extensively restored teeth, orthodontic appliances, peri/oral piercings, or removable partial dentures.
- Treatment with antibiotics within the 1-month period before the baseline examination, or a condition that is likely to require antibiotic treatment over the course of the trial.
- Chronic treatment (2 weeks or more) with any medication known to affect periodontal status (including phenytoin, calcium antagonists, cyclosporine, coumarin, nonsteroidal anti-inflammatory drugs, and aspirin) within 1 month of the baseline examination. All other medications for chronic medical conditions must have been initiated at least 3 months before enrollment.
- Have severe periodontal disease or being actively treated for periodontal disease.
- Having history of early-onset periodontitis or acute necrotizing ulcerative gingivitis.
- Concomitant periodontal therapy other than prophylaxis in the last 6 months.
- Professional prophylaxis within 1 month prior to the baseline clinical evaluation.
- Subjects who participated in a gingivitis study in the past month.
- Daily use of chemotherapeutic antiplaque/antigingivitis products such as

within the past 4 months.

- History of significant adverse effects following use of oral hygiene products such as toothpastes and mouthrinses.
- Subjects who are allergic to any ingredients in the test or control product, as listed on the IRB Safety Assessment.
- Self-reported pregnancy and nursing since hormonal changes can exaggerate gingival response to dental plaque.

#### VI. STUDY DESIGN

This parallel group, double-blind, randomized, single center, IRB/IEC-approved study will enroll approximately 320 subjects to ensure that approximately 100 subjects per group (300 subjects total) will complete the 6-month study. The Study Examiner will screen for subjects that meet the enrollment criteria. Subject group stratification will be based on smoking and tobacco use. Subjects will be randomly assigned to one of three dentifrice treatment groups. Oral soft and hard tissue examinations, gingivitis, bleeding and plaque assessments will be done at baseline and after 6 weeks and 3- and 6-months. Following an initial supervised tooth brushing, subjects will brush unsupervised with their assigned toothpaste at home for the 6-month treatment phase of the study, 2 times daily for 1 minute per brushing. Subjects will be provided with a timer and will maintain a daily diary of their brushing and record any oral effects they experience. Compliance will be assessed by subject diary and weight-loss of returned test products at each visit. The examiner will be blinded to the product codes/identification and product assignments.

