#### VII. SUBJECT ASSIGNMENT TO TREATMENT GROUPS

At the baseline visit, following the clinical assessments, the study population will be evenly distributed into three treatment groups of approximately equal size and equivalence. Qualified subjects will be randomly assigned to the three treatment groups based on a randomization scheme developed using the baseline plaque and gingival assessment scores and age for stratification. The study staff responsible for random assignments will be blinded to the product treatments. Allowance will be made for members of the same household co-habiting at one address to receive the same products to prevent inadvertent switch-over.

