#### X. STUDY PROCEDURE

#### Screening/Baseline Visit

Male and female subjects selected from the study site's database and prescreened potential subjects will report to the study site where they will read and sign the informed consent prior to enrollment. Subjects will be asked about demographics, medical history, general health status and current medication usage, and the information will be recorded. Prior to exam visit, subjects will refrain from oral hygiene the morning of their visit and will refrain from eating, drinking and smoking for approximately 4 hours prior to their visit.

The subjects will provide a sensory evaluation for safety purposes and they will fill out a product use questionnaire. They will be asked if they are currently experiencing any problems such as burning, stinging, irritation, etc., and if so, the nature of the effect, severity and onset time (if known) will be recorded on the CRF.

A qualified dental examiner will first perform an oral soft and hard tissue examination (OST), followed by a gingival assessment (Lobene Modified Gingival Index (MGI)), gingival bleeding assessment (Gingival Bleeding Index (GBI)) and plaque assessment (Soparkar Modification of the Turesky Modification of Quigley-Hein Plaque Index (PI)).

Next, qualified subjects will be given one tube of their randomly assigned dentifrice (baseline weight recorded), a toothbrush, timer, Subject Diary, and a Subject Instruction Sheet. They will be instructed to apply a ribbon of dentifrice along the entire length of the toothbrush bristles, and to brush 2 times daily (morning and evening) for 1 minute per brushing. Subjects will be given a timer to use for a timed 1 minute at home brushing and a diary to record the time of each brushing and any comments they may have about their brushing experience. To ensure that the subjects understand the use instructions, the subjects will do the first brushing at the site under supervision.

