#### Sample Size

The planned sample size for this study is to complete with at least 100 evaluable subjects per treatment group (300 total subjects). Approximately 320 subjects will be enrolled, to assure that at least 100 evaluable subjects per group complete the study. Based on a 3-month pilot clinical study, in which the coefficient of variation for the plaque index (PI) was 18.1%, the coefficient of variation for the gingival index (MGI) was 7.2%, and the coefficient of variation for the bleeding index (GBI) was 61.3%, 100 subjects per group will give a power of over 95% for detecting a 20% difference between groups.

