#### **Efficacy Analysis**

The primary analysis will be conducted on the population of subjects who complete all study visits. A secondary analysis will be conducted on the intent to treat population; that is, at each time point, all subjects who completed both the baseline evaluation and that evaluation will be included in the analysis. Additional subsets of the subject

population may be analyzed for informational purposes only. Other than the subject inclusion criterion, all analyses will be conducted identically as follows:

For each examination and each index, subjectwise mean Index scores will be obtained by calculating the average of the index scores evaluated at all individual measurement sites within the mouth. In addition to these 'whole-mouth' scores, subjectwise scores will also be obtained by calculating the average index scores over selected subsets of sites within the mouth. These subsets will include: Proximal sites; Marginal sites (MGI and GBI only); Gingival sites (PI only); Facial sites; Lingual sites; Posterior sites; Anterior Facial sites; and Anterior Lingual sites.

All statistical analyses will be based on the subjectwise Index scores. Separate analyses will be performed based on the subjectwise whole-mouth scores, as well as the subjectwise scores obtained from each of the selected subsets of the mouth.

The primary endpoints employed for the treatment comparisons in this study will be the month 6 Index scores. Additional analyses will be conducted on the Index scores collected at other time points. The comparison of the study treatments will employ an analysis of covariance (ANCOVA) model, with the associated baseline Index score included as a covariable. The ANCOVA model will include the factors: subject, treatment, and baseline Index score. Post-ANCOVA pairwise treatment comparisons of the adjusted means will be performed using t-tests utilizing Tukey's adjustment for multiple comparisons. Within-treatment comparisons of the mean baseline Index scores to the mean month 6 (or other post-baseline time point) Index scores will be performed using paired t-tests.

The comparison of the study treatments at baseline for each index will be performed using the same model described above, without the inclusion of the covariable.

All statistical tests of hypotheses will be two-sided, and employ a level of significance of  $\alpha = 0.05$ .

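### The protocol gives two stratification lists with no factor in common, and under either one the ANCOVA leaves out factors used to randomise

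*Combined protocol and SAP*

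**What the plan says.** Section VI (Study Design): "Subject group stratification will be based on smoking and tobacco use".

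Section VII (Subject Assignment to Treatment Groups): subjects are allocated by "a randomization scheme developed using the baseline plaque and gingival assessment scores and age for stratification". The same section allows people living together at one address to be given the same product.

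Section XIV, Efficacy Analysis: the treatment comparison is an ANCOVA "with the associated baseline Index score included as a covariable", and "The ANCOVA model will include the factors: subject, treatment, and baseline Index score". No part of section XIV mentions stratification.

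Two further places matter. The primary objective is safety and efficacy "in reducing gingival inflammation and bleeding", so the bleeding index is not a side outcome. The Screening/Baseline Visit text separates the two gingival measures: the tissue examination is "followed by a gingival assessment (Lobene Modified Gingival Index", that is, the MGI, and then comes a "gingival bleeding assessment (Gingival Bleeding Index", that is, the GBI.

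**The concern.** A site working from section VI and a site working from section VII would build different randomisation schedules. Both sentences are complete, so this is not a gap left by redaction or by reading the PDF.

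The analysis is affected too. Stratifying balances the arms on the chosen factors, which reduces the true variance of the treatment difference. A model without those factors leaves their contribution in the residual and reports a standard error that is too large. The precision that the design paid for is then not used. Any cost falls on the GBI, because PI and MGI have power to spare.

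**Working it through.** **1. Factors against model terms**

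| Reading of the stratification | In the ANCOVA | Missing from the ANCOVA |
|---|---|---|
| Section VI only | none | smoking and tobacco use, in every model |
| Section VII only | PI model: baseline PI. MGI model: baseline MGI. GBI model: baseline GBI, a stratifier only if the gingival scores include it | age in every model; gingival score in the PI model; plaque in the MGI model; at least plaque in the GBI model |
| Both together | as for section VII | as for section VII, plus tobacco use in every model |

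Factors are missing under every reading. The GBI row is open because the Screening/Baseline Visit text uses the gingival assessment label for the MGI, while section VII uses a plural that could cover both indices.

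**2. The plan's own figure**

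The plan gives no figure for the effect of stratification. The nearest is the Sample Size claim of over 95% power for a 20% difference with 100 per group, where "the coefficient of variation for the bleeding index (GBI) was 61.3" per cent, against 18.1% for PI and 7.2% for MGI. Difference/SE is 0.20/(CV × √(2/100)):

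- PI: 0.20/(0.181 × √0.02) = 7.8, power above 99.9%.
- MGI: 0.20/(0.072 × √0.02) = 19.6, power above 99.9%.
- GBI: 0.20/(0.613 × √0.02) = 2.31, power about 63% for a single t-test and 48% with Tukey.

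The claim therefore reproduces for PI and MGI but not for GBI. That shortfall belongs to the sample-size statement. Only the change in GBI power is counted here.

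**3. Leaving out balanced stratifiers**

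Inputs: 100 per arm; 300 − 4 = 296 residual degrees of freedom; critical values 1.968 (t) and 2.356 (Tukey, three groups). The subject factor is left out, because a month-6 analysis has one score per subject. R² is the share of the variance left after the index's own baseline that the omitted factors explain. No document gives it, so 0 to 15% is assumed.

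- Model SE / true SE = 1/√(1 − R²).
- Pairwise error = 2P(t > 1.968/√(1 − R²)).
- GBI power (noncentral t, 20% difference, Tukey) takes 61.3% as the residual CV, with the factors omitted (296 df) and then included (292 df).

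| R² | Model SE too large by | Pairwise error | Family-wise error | GBI power, omitted → included |
|---|---|---|---|---|
| 0 | 0 | 5.0% | 5.0% | no gain |
| 0.05 | 2.6% | 4.4% | 4.3% | 48.1% → 50.5% |
| 0.10 | 5.4% | 3.9% | 3.6% | 48.1% → 53.1% |
| 0.15 | 8.5% | 3.4% | 3.0% | 48.0% → 55.9% |

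At R² of 1 to 2% the gain is at most about 1 point. If baseline adjustment has already cut the residual CV, the gain over R² 0.05 to 0.15 is 2.3 to 7.2 points at 53.1% (baseline correlation 0.5) and 1.6 to 4.6 points at 43.8% (correlation 0.7).

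**4. Imperfect balance**

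The table assumes perfect balance, but plaque, gingival score and age are continuous and no cut-points are given. A median split of a normally distributed factor captures 2/π = 0.637 of its variance. At R² 0.15 the variance ratio is then 1 − 0.15 × 0.637 = 0.904, and the error is 2P(t > 1.968/√0.904) = 3.9%. Simulation gave 4.0 to 4.1% for a median split and 3.7 to 3.8% for tertiles.

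**5. Households**

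Assume 5 to 20% of subjects live in two-person study households, with correlation 0.1 to 0.5 after baseline adjustment. The design effect is 1 + share × correlation = 1.005 to 1.10, and the pairwise error is 5.1 to 6.2%. Combined with omitted stratifiers (R² 0.05 to 0.15) it is 3.4 to 5.5%.

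**The case against.** The strongest reply is that little may be lost. Neither section says its list is the only one, so they may be cumulative. The index's own baseline is probably the strongest predictor and is already in the model. The remaining factors may add nothing, and at R² = 0 the gain is nil. The direction is conservative, and the error figures shrink further if continuous factors are only coarsely balanced. All of this stands and sets the lower end of the range. It does not settle which factors were used or bring age or tobacco use into any model.

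Three stronger readings are tempting, and the documents do not support them.

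- *The trial cannot be analysed by the strata it randomises by.* Whoever runs the scheme will know which factors were used, and those can enter the model. The defect is that the plan does not fix them in advance.
- *The false-positive rate is inflated.* Omitting balanced prognostic factors lowers it. Only the household allowance pushes the other way. It is permissive, no household share is documented, and its assumed effect is small.
- *The Subject Identification section bars a household code, because the Sponsor may see only ID number and gender.* That section governs how subjects are identified to the Sponsor, not which data it receives. The demographic table already needs age and ethnic group, and the Sponsor's Statistician does the analysis.

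**Conclusion.** The point holds as an inconsistency in the text plus a modest loss of precision. Sections VI and VII must be reconciled, and under every reading the ANCOVA omits factors used to randomise.

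The size rests on an assumed R² of 0 to 15%. On that basis the GBI gains between nothing and about 8 points of power, the tests are somewhat conservative, and PI and MGI power is unaffected. The lower limit of 3.4% for the pairwise error also needs perfect balance; about 4.0% is more realistic at R² 15% if a continuous factor is only split at its median. The change should be made because it is nearly free and bleeding is in the primary objective. The household matter is secondary.

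**What to change.** 1. State one stratification list, in the same words, in sections VI and VII.
2. Say whether the gingival scores in section VII mean the MGI alone or the MGI and the GBI.
3. Give the categories or cut-points used for plaque, gingival score and age. Without them even a single list does not define a scheme.
4. Confirm that smoking and tobacco use are recorded at baseline. The questionnaire and medical history forms are not reproduced, so they may already hold this.
5. In Efficacy Analysis, add the factors actually used in randomisation to each ANCOVA, alongside treatment and the index's own baseline.
6. Optional: have the site supply a coded household identifier without an address, and run a sensitivity analysis with one member per household. The Subject Identification section needs no change for this.

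The cost is wording and roughly one to four model terms, depending on the list, out of about 296 residual degrees of freedom. PI, MGI, GBI and age are already collected. The optional step adds one coded column to the data file.
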